**Hospitalization, Prolonged Hospitalization or Surgery**

Any adverse event that results in hospitalization or prolonged hospitalization should be documented and reported as a serious adverse event unless specifically instructed otherwise in this protocol. Any condition responsible for surgery should be documented as an adverse event if the condition meets the criteria for and adverse event.

Neither the condition, hospitalization, prolonged hospitalization, nor surgery are reported as an adverse event in the following circumstances:

- Hospitalization or prolonged hospitalization for diagnostic or elective surgical procedures for a preexisting condition. Surgery should ***not*** be reported as an outcome of an adverse event if the purpose of the surgery was elective or diagnostic and the outcome was uneventful.
- Hospitalization or prolonged hospitalization required to allow efficacy measurement for the study.
- Hospitalization or prolonged hospitalization for therapy of the target disease of the study, unless it is a worsening or increase in frequency of hospital admissions as judged by the clinical investigator.

Routine Adverse Event Reporting

All Adverse Events must be reported in routine study data submissions. AEs reported through expedited SAE reports must also be reported in routine study data submissions (CRFs).

Adverse Event Case Report Form

All adverse events (regardless of grade and attribution) observed while on study and for 30 days after last dose of treatment, must be recorded on the adverse event case report form. After 30 days from last dose of treatment, only adverse events that are related to the study drug/combination are required to be recorded on the adverse event forms.

Reporting Requirements for Baseline Adverse Events:

A pertinent positive finding identified on baseline assessment is to be documented as a Baseline Adverse Event using CTCAE terminology and grade on the provided Baseline CRF. An expedited

AE report is not required if a patient is entered on to the study with a pre-existing condition (e.g., elevated laboratory value, diarrhea). The baseline AE must be re-assessed throughout the trial and reported if it fulfills expedited AE reporting guidelines.

- 1) If the pre-existing condition worsens in severity, the investigator must reassess the event to determine if an expedited report is required.
- 2) If the AE resolved and then recurs, the investigator must re-assess the event to determine if an expedited report is required.
- 3) No modification in grading is to be made to account for abnormalities existing at baseline.

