Dorgenmeltucel-L (HyperAcute Melanoma) immunotherapy consisting of equal cell doses of each of three allogeneic melanoma cancer cell lines engineered to express the murine  $\alpha(1,3)$ galactosyltransferase gene.

Dosage Treatment:

Arm 1 will receive either:

Arm 1A - ipilimumab at 3 mg/kg given every 3 weeks x 4 doses **or**

Arm 1B - nivolumab at 240 mg given every 2 weeks **or**

Arm 1C - pembrolizumab at 2 mg/kg given every 3 weeks **AND** 300 Million HAM cells per each immunization, given every week x 4, every 2 weeks for 5 months, every month for 6 months, and every 3 months x 4;

Arm 2 will receive either:

Arm 2A - ipilimumab at 3 mg/kg given every 3 weeks x 4 **or**

Arm 2B - nivolumab at 240 mg given every 2 weeks **or**

Arm 2C - pembrolizumab at 2 mg/kg given every 3 weeks

Clinical Endpoints:

1. Safety
2. Progression-free survival (PFS)
3. Overall response rate
4. Duration of objective response
5. Duration of stable disease
6. Overall survival (OS)
7. ████████████████████

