#### 4.4 *Duration of Therapy*

Patients whose tumor progresses on therapy will be off-study. However, mild progression ( $\leq 25\%$  increase in tumor size) at the beginning of the treatment is allowed, given the usual delayed response / pseudoproggression seen with immunotherapy (Wolchok et al., 2009).

Patients who experience a SAE which triggers stopping rules for immune checkpoint inhibitors ipilimumab, nivolumab, or pembrolizumab as described in their respective package inserts will be permanently discontinued from the immune checkpoint inhibitor. They can be continued on dorgenmeltucel-L (if in Arm 1) once recovered from immune checkpoint inhibitor toxicity.

Patients are also off study who:

- experience intercurrent illness that prevents further administration of treatment;
- decide to withdraw from the study;
- experience general or specific changes in the patient's condition that render them unacceptable for further treatment in the judgment of the investigator.

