### **Specific Risk/Adverse Events with ipilimumab**

Ipilimumab can result in severe and fatal immune-mediated adverse reactions due to T-cell activation and proliferation. These immune-mediated reactions may involve any organ system; however, the most common severe immune-mediated adverse reactions are enterocolitis, hepatitis, dermatitis (including toxic epidermal necrolysis), neuropathy, and endocrinopathy. The majority of these immune-mediated reactions initially manifested during treatment; however, a minority occurred weeks to months after discontinuation of ipilimumab.

Permanently discontinue ipilimumab and initiate systemic high-dose corticosteroid therapy for severe immune-mediate reactions. Assess patients for signs and symptoms of enterocolitis, dermatitis, neuropathy, and endocrinopathy and evaluate clinical chemistries including liver function tests and thyroid function tests at baseline and before each dose. For specific details of toxicity management, the treating physician is instructed to refer to the package insert for ipilimumab and to follow the instructions and algorithms therein.

Specific attention to development of autoimmune events during periodic study visits can be evaluated by an optional checklist provided in **Appendix E**. This checklist in addition to the serologic tests obtained can be used by the study physicians to determine if further evaluation for autoimmune disease is warranted by an appropriate specialist in the organ system affected. This can be done to avoid misinterpretation of spurious autoimmune test results.

Trials using immunomodulatory agents such as ipilimumab CTLA-4 have shown a correlation between disease response and so called autoimmune breakthrough events (ABEs) like hypophysitis, colitis, autoimmune hepatitis, or dermatitis. It is for this reason that they are distinguished from other adverse events.

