**Safety Analyses**

Adverse events will be summarized by MedDRA system organ class and preferred term. Separate tabulations will be produced for all treatment-emergent adverse events, treatment-related adverse events (those considered by the Investigator as at least possibly drug related), serious adverse events, discontinuations due to adverse events, and adverse events of at least Grade 3 severity. By-patient listings will be provided for deaths, serious adverse events, and events leading to discontinuation of treatment.

Descriptive statistics will be provided for clinical laboratory data and vital signs data, presented as both actual values and changes from baseline relative to each on-study evaluation and to the last evaluation on study.

In addition, shift tables of laboratory data from baseline to worst value on treatment will be presented based on CTCAE v 4.03 grading.

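### In the ipilimumab stratum, all-cause adverse events may be collected about twice as long with vaccine as without; the protocol's passages conflict, and the planned crude safety tables make no allowance for it

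*Combined protocol and SAP*

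**What the plan says.** **Collection rule.** The adverse event case report form paragraph of Section 10.6 asks for all events, whatever the grade or attribution, "observed while on study and for 30 days after last dose of treatment". It continues: "After 30 days from last dose of treatment, only adverse events that are related to the study drug/combination are required to be recorded".

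**Dosing in the ipilimumab stratum.** The synopsis gives "Arm 2A - ipilimumab at 3 mg/kg given every 3 weeks x 4". The Arm 2A schema places these doses on Days 1, 22, 43 and 64, then has patients observed for progression and taken off study when it occurs. Arm 1A adds vaccine "given every week x 4, every 2 weeks for 5 months, every month for 6 months, and every 3 months x 4", which is 4 + 10 + 6 + 4 = 24 immunizations, ending at month 24.

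**Calendars (Section 8).** The Arm 1A adverse event line runs throughout the study and follow-up. The Arm 2A line covers the Week 1 to 13 grid and the first follow-up visit. After that visit, assessments other than imaging and survival checks are left to standard of care.

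**Other strata.** Nivolumab and pembrolizumab continue in both arms until progression or toxicity. For patients who permanently stop the checkpoint inhibitor because of toxicity, Section 4.4 says: "They can be continued on dorgenmeltucel-L (if in Arm 1) once recovered from immune checkpoint inhibitor toxicity".

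**Analysis.** Safety is a primary objective, compared between arms (Section 1.1.1). Under Safety Analyses in Section 12.3, "Separate tabulations will be produced for all treatment-emergent adverse events", and likewise for related, serious, Grade 3 or higher and discontinuation events. Laboratory shift tables run from baseline to the worst on-treatment value. The general format is numbers and percentages of patients. No common window, time-at-risk denominator or time-to-event summary of adverse events is stated.

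**The concern.** A crude percentage of patients with an event depends on how long each patient is watched. If the end of all-cause collection follows the last dose of any study treatment, and one arm has up to 24 months of vaccine while the other has four infusions, the longer-dosed arm accumulates more events of every kind, including those unrelated to treatment. The worst-value shift tables have the same weakness, because the worst of many samples is on average worse than the worst of few.

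At stake is the comparative reading of a primary objective. An apparent excess of toxicity in Arm 1 could reflect observation time alone, and no planned table would separate the two. If the vaccine delays progression, its patients are watched longer still and the distortion grows.

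**Working it through.** The protocol gives no figure for the length of adverse event observation. The progression inputs come from Section 12.1: control median 3 months, hazard ratios 0.6895 and 0.6435, 96 events, two-sided alpha 0.20. That section's power statement reproduces: Φ(√(96/4) × |ln HR| − 1.2816) gives 70.5% and 81.0%, against 70% and 80% stated.

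**1. Full course, narrower reading.**
- Arm 2A: Day 64 + 30 = Day 94.
- Arm 1A: month 24 (about Day 730) + 30 = about Day 760.
- Ratio: 760/94 = 8.1. Few patients reach this under a 3-month median.

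**2. Mean window, narrower reading, equal PFS.** Assume exponential PFS with rate λ = ln 2/3 = 0.231 per month and dosing stopped at progression. The mean window is (1 − e^(−λL))/λ plus 30 days (0.99 month), where L is the time to the last planned dose.
- Arm 1A, L = 24: 4.33 × (1 − 0.004) + 0.99 = 5.3 months.
- Arm 2A, L = 63 days = 2.07 months: 4.33 × (1 − 0.620) + 0.99 = 2.6 months.
- Ratio: about 2.0.

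A simulation that follows the schema dosing days gives 152 against 77 days (1.97) if progression is detected at once, and 194 against 94 days (2.06) if it is detected at scheduled scans.

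**3. With a vaccine effect (HR 0.6435).** λ = 0.149 in Arm 1A gives 6.73 × (1 − 0.028) + 0.99 = 7.5 months against 2.6, a ratio of 2.9. The simulation gives 2.80 and 2.67 under the two detection rules.

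**4. On-study reading.** If Arm 2A collection continues to progression, the simulated ratio under equal PFS falls to 1.07–1.08.

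**5. PD-1 strata and whole arms, narrower reading, equal PFS.** The simulated ratio is 0.99–1.00 for nivolumab and 1.03 for pembrolizumab. The ipilimumab share is not given, so it is varied. With immediate detection, PD-1 windows average about 157 days in Arm 1 and 154.5 in Arm 2 (156 for nivolumab, 153 for pembrolizumab):

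| Assumed ipilimumab share | Arm 1 mean (days) | Arm 2 mean (days) | Ratio |
|---|---|---|---|
| 10% | 0.10 × 152 + 0.90 × 157 = 156.5 | 0.10 × 77 + 0.90 × 154.5 = 146.8 | 1.07 |
| 25% | 155.8 | 135.1 | 1.15 |
| 50% | 154.5 | 115.8 | 1.33 |

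With detection at scheduled scans the 50% case is 1.35, so about 1.34 overall.

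**6. Effect on crude percentages, Arm 1A against Arm 2A.** Assume the same constant hazard in both arms, 20% per 90 days, and equal PFS. The proportion with at least one event is the mean of 1 − e^(−hazard × window): 28.7% against 17.3% with immediate detection, 36.2% against 20.8% with scheduled scans. At 10% per 90 days it is 15.5% against 8.6%, and at 30% it is 40.1% against 26.0% (immediate detection). A rate per unit of time at risk would give a ratio of 1 in each case.

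**7. Laboratory sampling.** As the calendars read after extraction, Arm 1A has 18 scheduled on-study blood counts to month 24 (Weeks 1, 4, 7, 10, 13, 16, 20 and 24; months 7 to 12; months 15, 18, 21 and 24). Arm 2A has 5 (Weeks 1, 4, 7, 10 and 13) before the first follow-up visit. The schedules agree through Week 13; the difference affects patients who continue beyond it.

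**The case against.** **The on-study clause.** The strongest objection is that Section 10.6 also covers events while on study, and the Arm 2A schema keeps patients on study until progression. On that reading the imbalance almost disappears (ratio 1.07–1.08). This stands as a legitimate reading. It does not settle the matter: the next sentence of Section 10.6 restricts recording 30 days after the last dose, and the two calendars follow that restriction. For an Arm 2A patient who has not progressed, sites could apply either rule.

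**Scope.** The protocol itself says in Section 2.5 that practice is moving towards PD-1 inhibitors, so the ipilimumab stratum may be small and the pooled distortion modest. This stands.

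**Late immune events.** Section 5.2 says that of the immune-mediated reactions "a minority occurred weeks to months after discontinuation of ipilimumab", and a reader might infer that such events are lost in Arm 2A. The documents do not support that. Section 10.4 attributes events already known for a checkpoint inhibitor to that drug, and related events are recorded after 30 days with no end date. The treatment-related tables are therefore less affected, provided the reference in Section 10.6 to the study drug or combination is taken to include a checkpoint inhibitor given alone.

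**Constant hazard.** Section 5.2 also says that most of these reactions first appeared during treatment. A front-loaded hazard would narrow the gaps in step 6, so those percentages are illustrations, not forecasts.

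**Descriptive purpose.** No safety hypothesis test is planned, and events during two years of vaccination belong to that regimen's safety profile. That is a reason to keep the crude tables. It does not make them a fair comparison of arms watched for different lengths of time.

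**Conclusion.** The point holds for the ipilimumab stratum, conditional on how Section 10.6 is read. On the narrower reading, with exponential PFS, a 3-month median and no PFS effect, Arm 1A is watched about twice as long as Arm 2A, and about 2.7 to 2.9 times as long at HR 0.6435. On the on-study reading there is little imbalance under equal PFS. The text does not say which applies, and that conflict is itself a defect.

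Two stronger readings are tempting. One is that vaccine patients as a whole are watched twice as long as controls; the PD-1 strata are near 1.0 and the pooled ratio is about 1.07 to 1.34 over assumed ipilimumab shares of 10% to 50%. The other is that the same gap opens in every stratum because Arm 1 patients may stay on vaccine after stopping the checkpoint inhibitor. Section 4.4 does allow that, but its size cannot be estimated from the documents, and stopping the inhibitor for toxicity is not by itself listed as a reason to leave the study, so an Arm 2 patient's window need not close 30 days later.

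Within these limits, the direction is consistent: crude all-cause percentages and worst-value shift tables would tend to show more toxicity in Arm 1 even if the vaccine adds none. The point should be addressed before the safety tables are finalised.

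**What to change.** 1. Reconcile the adverse event paragraph of Section 10.6, the Arm 2A schema and the Arm 1A and 2A calendars, so that both arms use the same all-cause collection period. Count it from randomization or first study dose, and make it independent of when dosing stops. State that related events after that period include those related to a checkpoint inhibitor given alone.
2. In Section 12.3, keep the crude tables. Add, overall and by checkpoint inhibitor: incidence per patient-month at risk; cumulative incidence (time to first event) of Grade 3 or higher events; and adverse event and laboratory shift summaries over a common fixed window from randomization or first study dose.
3. Do not start the clock at the first checkpoint inhibitor dose. In Arm 1A that is Day 22, and under the 3-month model 1 − 2^(−0.69/3), about 15%, would have progressed by then (21 days = 0.69 month). The comparison would no longer be between the groups as randomized, and the vaccine-only weeks would drop out of it.

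The cost is protocol wording, a few extra tables and limited additional adverse event recording during Arm 2A follow-up. No treatment changes.

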#### Other Reporting Requirements:

In addition to the clinical monitoring as outlined in the Study Calendars, monitoring for long-term or delayed adverse events related to gene transfer (required at least yearly for 15 years by the FDA-BRMAC) will be the responsibility of the Principal Investigator at each site. Each PI will be responsible for the recording and reporting of this information to the sponsor. Investigators must report the emergence of new clinical conditions, specifically:

- 1) New malignancy(ies);
- 2) New incidence or exacerbation of a pre-existing neurologic disorder;
- 3) New incidence or exacerbation of a prior rheumatologic or other autoimmune disorder;
- 4) New incidence of a hematologic disorder;
- 5) Unexpected illness and hospitalizations;
- 6) Expected or unexpected death and cause of death.

For the first 5 years, we recommend that Principal Investigators schedule a visit with each study subject to record new findings including history, physical examination, or laboratory testing at least once a year, even if the subject is off study. For the subsequent 10 years, we recommend that Investigators contact subjects by telephone or written questionnaire at least once a year to gather new information.

## **11 Human Subjects Protections**

### ***11.1 Rationale for Subject Selection***

Melanoma is a common cancer that affects both genders and all racial/ethnic groups. Subjects from both genders and all racial/ethnic groups are eligible for this study if they meet the eligibility criteria. We will make an attempt at enrolling representative proportions of women and minorities on this study. However, darker skin pigmentation is a significant protective factor for the development of melanoma. The incidence of melanoma in Blacks is more than 30-fold lower than Caucasians. This would necessarily mean that African-Americans and other ethnic groups with darker skin pigmentation will be under represented in patients eligible for this study.

To date, there is no information that suggests differences in immunization or disease response would be expected in one group compared to another. Efforts will be made to extend accrual to a representative population, but in this phase 2 study, a balance must be struck between patient safety considerations and limitations on the number of individuals exposed to potentially toxic and/or ineffective treatments on the one hand and the need to explore gender and ethnic aspects of clinical research on the other hand. In this small phase 2 trial it is unlikely that significant differences in outcome would be detected that correlate with gender or racial/ethnic identity. If differences in

outcome that correlate to gender or to racial/ethnic identity are noted, a follow-up study may be written to investigate those differences more fully.

### ***11.2 Participation of Children***

The occurrence of melanoma in individuals less than 18 years of age is rare and usually associated with congenital dysplastic nevus syndromes. Minors below the age of 18 will not be eligible for this protocol because of the limited information available on the effects and toxicity of anti-tumor vaccines in children, in particular the extremely limited information concerning allogeneic expression of  $\alpha(1,3)$ GT in adults, and the complete lack of safety information on these reagents in children.

### ***11.3 Evaluation of Benefits and Risks***

The benefits of this immunization approach are theoretical and it is hoped that the induction of an acute rejection response to the  $\alpha(1,3)$ galactosylated residues on the allogenic melanoma cancer cells used to immunize the patient will lead to cross-recognition of weak native tumor antigens on the patient's melanoma cells that may be shared with the genetically engineered immunotherapy cells. By generating an antibody and cellular immune response against the patient's tumor, it is hoped that the patient may benefit by a tumor response.

Given the safety demonstrated with transfer of murine retroviral vector producer cells in several studies that naturally express the  $\alpha(1,3)$ GT enzyme and have 1,3- $\alpha$ -galactosylated residues, and the poor prognosis of this patient population, it is believed that the possible benefits from tumor response and improved survival probability far outweigh the risk to the patient. The information obtained in this study may be extremely valuable in the treatment of melanoma and other malignancies in the future. The patients to be entered in this protocol have refractory or recurrent melanoma and limited life expectancies. The chance of this experimental treatment to provide clinical benefit is unknown. All possible benefits and known risks will be carefully explained to all patients and an Informed Consent Document will be signed by the patient prior to entrance into the protocol.

There are no anticipated serious adverse side effects to the immunization technique employed in this study. Theoretical risks may include the induction of unanticipated autoimmune disease and/or liver, kidney, lung, heart and CNS damage and/or coagulopathy and bleeding as a result of excessive activation of the complement (C') system. Expected risks and discomforts to the patients are minimal and will be those of needle sticks and phlebotomy. An acceptable adverse event profile was developed in the Phase I part of the trial. Patients will be observed for one hour after each immunization for allergic/hypersensitivity reactions. Patients will be treated as deemed medically appropriate for any immediate or delayed adverse event related to the immunization.

Five similar instances involved the development of an aggressive T-cell acute lymphocytic leukemia (T-ALL) that contain a vector proviral insertion at a chromosomal translocation breakpoint in three children that underwent *ex vivo* transduction of CD34+ hematopoietic stem cells with a Moloney-based retroviral vector in a clinical trial for the treatment of X-SCID. While most children who participated in this clinical trial appear to have been cured of their disease (18 out of 20), five children developed the leukemia approximately 2 to 5 years after their gene

therapy treatment. Extensive testing was done to determine the cause of the leukemia, and it was found that the virus used to deliver the X-SCID gene disrupted a normal gene in the bone marrow cells that then lead to the development of leukemia. One of these children has since died of their leukemia, and the long-term prognosis of the other children is unknown at this time.

These AE's are not believed to be relevant to the present trial. This trial involves neither the use of adenoviruses, the direct administration of live retrovirus, or live transduced cells to the patient. The *ex vivo* allogeneic immunotherapy cells transduced by our vector are nonviable after being irradiated.

